#### 8.5 Progression-Free Survival

Progression-Free Survival (PFS) is defined as the duration of time from start of treatment to time of objective disease progression (including initiation of new therapy or death). Follow-up will continue until disease progression, which we anticipate to be no more than 2 years.

#### 8.6 Quality of Life

Quality of Life (QOL) score on the SF-36 survey will be measured at the start of each cycle for each patient and results for the entire patient group will be provided in a descriptive fashion without formal statistical analysis

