### 1.1.7 Secondary Objectives:

- To assess progression free survival (defined as the interval from the first documentation of CR, VGPR or PR to the earlier of the first documentation of disease progression)
- To determine organ response (defined as improvement of involved organ function i.e. eGFR for kidneys, EF for heart etc.)
- To assess the safety and tolerability of idelalisib
- To measure impact on QOL of life using SF-36 assessment tool.

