#### 4.1.4 Duration of Participation

Participants will continue to take Idelalisib per-protocol until disease progression or unacceptable adverse event. Study visits will occur two weeks after starting Idelalisib, then monthly from the start of Idelalisib for three months, followed by every three months from the start of Idelalisib thereafter until disease progression or the start of another line of therapy, whichever occurs first. For patients who have responded but come off Idelalisib for reasons other than progression, they will be followed every 6 months until progression or another line of therapy. An end of study visit will take place 30 days following the last dose of Idelalisib. The duration for individuals, and duration of the study, are dependent upon disease response. We anticipate no more than 2 years duration for individual subjects. We anticipate the study will remain active for a total of 4 years including enrollment, treatment, follow-up and data analysis.

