## 7.0 STUDY CALENDAR

	At enrollment	Every 2 weeks for 3-6 months after starting Idelalisib 	One and two months after starting Idelalisib 	Monthly while taking Idelalisib	Every three Months 	End of Study Treatment Visit 
PHYSICAL						
History & Physical Exam	X				X	X
Height & Weight	X					
ECOG Performance Status (see Appendix A)	X		X		X	X
Adverse Event Monitoring			X		X	X
SF-36 (QOL)	X		X		X	
LABORATORY-Serum						
Complete Blood Count with Differential	X	X 	X		X	X
Beta-HCG 	X					
Chemistry including: BUN, creatinine, glucose, sodium, potassium, chloride, bicarb, cholesterol, CK, calcium, total protein, LDH, magnesium, phosphorous, triglycerides, uric acid, TSH, amylase	X		X		X	X
BUN / Serum Creatinine	X		X		X	X
Hepatic Function Testing: ALT/AST, Bilirubin, Albumin, Alkaline Phosphatase	X	X 	X		X	X
β-2 Microglobulin / C-reactive protein	X		X		X	
Cardiac enzymes: BNP/ Troponin I	X		X		X	
Serum free light chain assay	X		X		X	
SPEP, SIFE, Immunoglobulins	X		X		X	
Vitamin B12, folate, ESR, retic %	X		X			
Coagulation profile: PTT, INR, D-dimer, Factor X	X		X		X	
Hepatitis Serologies: Hep B Surface Antigen, Hep B Core antibody, Hep C Antibody	X					
HIV antibody- 1+2	X					
CMV PCR	X			X		
1, 3 β-D-glucan	X			X		
LABORATORY-Urine						
Urinalysis	X				X	
24 hour urine: total protein, creatinine, kappa, and lambda	X				Every 6 months	
UPEP / UIFE / TV	X				X	
PATHOLOGY						
BM biopsy w/ MYD88 and CXCR4 WHIM analysis 	X					
FISH for t(11;14)	X					
Fat aspirate (if not previously done)	X					
X-RAYS AND SCANS						
ECG / CXR	X					
Echocardiogram	X				Every 6 months	
PFTs	X					

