For women of childbearing potential only: Serum pregnancy test is required at screening.If bone marrow biopsy and aspiration must have been repeated following any previous therapy > 1 cycle.These visits including physical exam and blood work may be performed by local physician and confirmed by telephone contact if patient unable to return for week 2 visit or monthly visits on months 1 and 2.CBC with differential should be monitored every 2 weeks for the first 6 months of treatmentHepatic function tests should be checked every 2 weeks for the first 3 months of treatmentWhile on study drug or until disease progression or start of another therapy.30 days following last dose (+/-) 7 days.

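### SF-36 timing in section 8.6 and the study calendar disagree after month 3, and no form is scheduled at the end-of-treatment visit, so patients who progress or stop early may leave no score after stopping

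*Combined protocol and SAP*

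**What the plan says.** Quality of life is a secondary objective. Section 1.1.7 of the protocol words it as "To measure impact on QOL of life using SF-36 assessment tool", and section 12.1 lists it again among the secondary endpoints.

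Two places set the timing of the questionnaire:

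- Section 8.6 says the "Quality of Life (QOL) score on the SF-36 survey will be measured at the start of each cycle for each patient". On reporting it adds that "results for the entire patient group will be provided in a descriptive fashion without formal statistical analysis".
- The study calendar in section 7.0 marks SF-36 at enrolment, in the column headed "One and two months after starting Idelalisib", and in the three-monthly column. It leaves SF-36 blank in the column headed "Monthly while taking Idelalisib" and at the End of Study Treatment Visit.

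Three further statements bear on this:

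- Section 4.1.4 places study visits at week 2, "then monthly from the start of Idelalisib for three months, followed by every three months from the start of Idelalisib thereafter".
- Calendar footnote 6 says the three-monthly column runs "While on study drug or until disease progression or start of another therapy".
- Calendar footnote 7 places the end-of-treatment visit "30 days following last dose (+/-) 7 days".

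**The concern.** A site cannot follow both schedules. One asks for a form every cycle. The other, from month 4 on, offers a form only every third month, and the visit plan matches the second.

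The blank at the end-of-treatment visit matters more for interpretation. That visit already includes a physical examination, performance status, adverse event review and laboratory tests, so the patient is being assessed anyway. Without a form there, and with three-monthly collection ending at progression or new therapy, the patients most likely to be doing badly are the ones whose state after stopping goes unrecorded.

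Section 8.6 promises results for the whole group. It does not say how missing forms are handled, nor that the number behind each summary will be shown. Later summaries could then look better than the group as a whole because of who remains in them. A form not collected at discontinuation cannot be recovered afterwards.

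**Working it through.** The plan gives no figure to reproduce here, so the check is a count of forms and a comparison of the sections.

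**Inputs**

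- Per-cycle rule: section 8.6.
- Calendar rule: months 0, 1, 2, then 3, 6, 9 and so on (section 7.0, consistent with section 4.1.4).
- Maximum time on study: 2 years anticipated (section 4.1.4).
- Cycle length: not defined in days. Section 6.1.4 dispenses one cycle of tablets at monthly visits and three cycles at three-monthly visits, so one cycle is taken as one month. This is an assumption.

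**Count of forms due at cycle starts, before the end of each period**

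| Period | Section 8.6 | Calendar | Cycle starts with no calendar form |
|---|---|---|---|
| 3 months | 3 | 3 | 0 |
| 6 months | 6 | 4 | 2 (months 4, 5) |
| 12 months | 12 | 6 | 6 |
| 24 months | 24 | 10 | 14 |

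For 24 months, section 8.6 gives months 0 to 23, which is 24 forms. The calendar gives months 0, 1, 2, 3, 6, 9, 12, 15, 18 and 21, which is 10. The difference is 24 − 10 = 14. Counting a month-24 form on both sides gives 25 against 11, with the same difference. If a cycle were 28 days, section 8.6 would call for 27 forms over two years and the gap would widen.

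**Age of the last score at stopping, on the calendar schedule**

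- Stopping before month 3: at most about one month old. A patient who stops before month 1 has only the baseline form.
- Stopping after month 3: up to almost three months old.

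**Who has a form scheduled after stopping**

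- Patients who progress and stop: footnote 6 ends the three-monthly column, and the end-of-treatment visit has no form. None is scheduled.
- Responders who stop without progression: section 4.1.4 follows them every six months without listing procedures, whereas footnote 6 can be read as continuing three-monthly forms. The two are not aligned.
- Non-responders who stop for toxicity: section 4.1.4 names no off-drug follow-up for them beyond the end-of-treatment visit, and sections 5 and 5.1.1 take a patient with a long toxicity delay off the study. On that reading no form follows. Read literally, footnote 6 would still give them forms until progression or new therapy.

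**Rough scale**

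With 18 patients (section 1.1.5), each is 1/18 = 5.6% of the group. Section 2.1.6 reports discontinuation for adverse events of 12% in studies 101-02/101-99 and 15% in study 101-09. Applied here, that is 0.12 × 18 = 2.2 to 0.15 × 18 = 2.7, or about 2 to 3 patients, before any losses to progression. This is illustrative only: those studies enrolled other diseases, at other doses.

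**The case against.** The strongest reply is that this is a drafting mismatch in an untested endpoint. Section 8.6 rules out formal analysis, so no decision depends on SF-36. The two schedules are identical through month 3. The end-of-treatment visit also omits free light chains and cardiac markers, so it looks like a deliberate safety visit rather than one where a form was forgotten. And a form at that visit, about a month after the last dose, would not measure quality of life at the moment of stopping. All of this stands. It limits the weight of the point but does not reconcile the two schedules, and it does not supply a score for patients who leave.

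A reader might also infer more than the documents support:

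- *That reported quality of life would reflect only patients still on drug.* Footnote 6, read literally, continues the three-monthly form off drug until progression or another therapy. Section 4.1.4 keeps responders who stop in follow-up. Sections 4.1.3 and 5.1.1 let some patients who meet progression criteria stay on protocol.
- *That many patients would have no score near discontinuation, because median exposure was 3.3 to 3.6 months in two earlier studies.* Exposure that short points the other way: about half the patients would stop during or just after the monthly phase, with a last score no more than about one month old. Those two studies were also small, and in study 101-09 86 of 125 (69%) were exposed for more than four months.
- *That group means will drift upward.* This is a plausible direction. Nothing in the documents allows its size to be estimated.

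**Conclusion.** The point holds as a minor one with two parts. First, section 8.6 and the calendar contradict each other on SF-36 timing after month 3: 24 against 10 forms over two years (25 against 11 with month 24), assuming one-month cycles. The visit plan in section 4.1.4 cannot accommodate the larger number. Second, no SF-36 is scheduled at the end-of-treatment visit or after progression or new therapy. Patients who progress and stop, and possibly non-responders who stop for toxicity, may leave no score after stopping, and later descriptive summaries would be weighted towards patients without progression. How far this reaches toxicity stoppers depends on how footnote 6 is read against section 4.1.4. The consequence is confined to the interpretation of one descriptive secondary endpoint; the response-rate conclusion is untouched.

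**What to change.** 1. Reword section 8.6 to the calendar schedule: enrolment, months 1 and 2, then every three months.
2. Add SF-36 to the existing End of Study Treatment Visit. Because footnote 7 puts that visit between 23 and 37 days after the last dose (30 − 7 to 30 + 7), describe the score as quality of life shortly after stopping, and flag it if new therapy has begun.
3. State whether SF-36 is collected in off-drug follow-up, so that footnote 6 and section 4.1.4 agree.
4. In the report, show the number of patients contributing at each time point. Beside the time-point summaries, give change from baseline to the last available score for all treated patients, stating how many have a baseline form only.

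The cost is one more questionnaire per patient at a visit that already takes place, plus a small text amendment. No new visit, test or sample size change is needed.

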### 9. ADVERSE EVENTS

#### 9.1 Serious Adverse Event (SAE) Definition

A serious adverse event is one that at any dose (including overdose):

- Results in death
- Is life-threatening
- Requires in-patient hospitalization or prolongation of existing hospitalization
- Results in persistent or significant disability or incapacity
- Is a congenital anomaly or birth defect
- Is an important medical event
- Suspected positive Pregnancy

“Life-threatening” means that the subject was at immediate risk of death at the time of the serious adverse event; it does not refer to a serious adverse event that hypothetically might have caused death if it were more severe.

“Persistent or significant disability or incapacity” means that there is a substantial disruption of a person’s ability to carry out normal life functions.

Medical and scientific judgment should be exercised in deciding whether expedited reporting is appropriate in situations where none of the outcomes listed above occurred. Important medical events that may not be immediately life-threatening or result in death or hospitalization but may jeopardize the subject or may require intervention to prevent one of the other outcomes listed in the definition above should also usually be considered serious. Examples of such events include allergic bronchospasm requiring intensive treatment in an emergency room or at home, blood dyscrasias or convulsions that do not result in in-patient hospitalization, or the development of drug dependency or drug abuse. A new diagnosis of cancer during the course of a treatment should be considered as medically important

 The pregnancy itself is not considered an AE nor is an induced elective abortion to terminate a pregnancy without medical reasons.

Any premature termination of pregnancy (eg, a spontaneous abortion, an induced therapeutic abortion due to complications or other medical reasons) must be reported within 24 hours as an SAE. The underlying medical reason for this procedure should be recorded as the AE term. A spontaneous abortion is always considered to be an SAE and will be reported as described in Section 9.2. Furthermore, any SAE occurring as an adverse pregnancy outcome post study must be reported to Gilead DSPH.

Unexpected fatal or life-threatening and related experiences associated with the use of the study treatment will be reported to Gilead Sciences within three business days of awareness of the event. All other serious experiences (regardless of expectedness) associated with the use of the study treatment will be reported to Gilead Sciences within seven business days of awareness of the event.

The Investigator must submit each IND safety report in a narrative format or on FDA Form 3500A to the company at the Gilead Sciences Drug Safety department:

Gilead Sciences Drug Safety & Public Health	
Address:	[name]
US Local [contact]
US Local [contact]
E-mail	[contact]

Upon request from the FDA or Gilead Sciences additional data or information that the agency or Gilead Sciences deems necessary, must be reported as soon as possible but no later than 15 calendar days.

## 9.2 Adverse Drug Reaction Reporting

Toxicity will be scored using CTCAE Version 4.03 for toxicity and adverse event reporting. A copy of the CTCAE Version 4.03 can be downloaded from the CTEP homepage (<HTTP://CTEP.INFO.NIH.GOV>). All appropriate treatment areas should have access to a copy of the CTCAE Version 4.03. All adverse clinical experiences, whether observed by the investigator or reported by the subject, must be recorded, with details about the duration and intensity of each episode, the action taken with respect to the test drug, and the subject's outcome. The investigator must evaluate each adverse experience for its relationship to the test drug and for its seriousness.

The investigator must appraise all abnormal laboratory results for their clinical significance. If any abnormal laboratory result is considered clinically significant, the investigator must provide details about the action taken with respect to the test drug and about the subject's outcome.

AEs and SAEs will be reported from the first dose of study drug through 30 days after administration of the last dose of study drug or the start of subsequent therapy for amyloidosis, whichever occurs first. All SAEs should continue to be monitored until they are resolved or are clearly determined to be due to a patient's stable or chronic condition or intercurrent illness(es).

## 9.3 Monitoring of Adverse Events and Period of Observation

All adverse events, both serious and non-serious, and deaths that are encountered from initiation of study intervention, throughout the study, and within 30 days of the last study intervention should be followed to their resolution, or until the participating investigator assesses them as stable, or the participating investigator determines the event to be irreversible, or the participant is lost to follow-up. The presence and resolution of Grade 2 or higher AEs and SAEs (with dates) should be documented on the appropriate case report form and recorded in the participant's medical record to facilitate source data verification.

For some SAEs, the study sponsor or designee may follow-up by telephone, fax, and/or monitoring visit to obtain additional case details deemed necessary to appropriately evaluate the SAE report (e.g., hospital discharge summary, consultant report, or autopsy report).

## 10. DATA MANAGEMENT

### 10.1 Analyses and Reporting

Data will be analyzed and reported after study is completed or meaningful endpoints are reached. All subsequent data collected will be analyzed and reported in a follow-up clinical report.

### 10.2 Data Monitoring Committee

Toxicity and accrual monitoring will be performed on a routine basis by the study investigators as well as the multidisciplinary members of the Amyloid Center at Boston University, which has over 40 years' experience in the treatment of AL amyloidosis. Subjects will undergo toxicity assessment, performance status assessment and laboratory tests according to the study calendar in Section 7. Organ response assessment will be conducted every six cycles. The clinical status and laboratory reports of the study participants will be reviewed routinely by the co-investigators at the weekly meetings of the Amyloid Program. Dose modifications/interruptions or discontinuation will be implemented according to Section 5.

In addition, the BMC Cancer Center's Internal Data and Safety Monitoring Committee (DSMC) will review the protocol, and will determine review frequency based on level of risk. The protocol will be reviewed at least annually by the DSMC. Please see full DSMB Charter in Appendix B.

### 10.3 Study monitoring and auditing

Investigator responsibilities are set out in the ICH guideline for Good Clinical Practice (GCP) and in the US Code of Federal Regulations.

Investigators must enter study data onto CRFs or other data collection system. The Investigator will permit study-related monitoring visits and audits by Gilead or its representatives, IRB/EC review, and regulatory inspection(s) (e.g., FDA, EMEA, TPP), providing direct access to the facilities where the study took place, to source documents, to CRFs, and to all other study documents.

## 11.0 REGULATORY CONSIDERATIONS

### 11.1 Protocol Amendments

Any amendment to this protocol must be agreed to by the Principal Investigator and reviewed and approved by Gilead. Amendments should only be submitted to IRB/EC after consideration of Gilead review. Written verification of IRB approval will be obtained before any amendment is implemented.

### 11.2 Protocol deviations

When an emergency occurs that requires a deviation from the protocol for a subject, a deviation will be made only for that subject. A decision will be made as soon as possible to determine whether or not the subject (for whom the deviation from protocol was effected) is to continue in the study. The subject's medical records will completely describe the deviation from the protocol and state the reasons for such deviation. In addition, the Investigator will notify the IRB in writing of such deviation from protocol. Non-emergency minor deviations from the protocol will be permitted with approval of the Principal Investigator.

### 11.3 Institutional Review Board/Ethics Committee approval

The protocol for this study has been designed in accordance with the general ethical principles outlined in the Declaration of Helsinki. The review of this protocol by the IRB/EC and the performance of all aspects of the study, including the methods used for obtaining informed consent, must also be in accordance with principles enunciated in the declaration, as well as ICH Guidelines, Title 21 of the Code of Federal Regulations (CFR), Part 50 Protection of Human Subjects and Part 56 Institutional Review Boards.

The Investigator will be responsible for preparing documents for submission to the relevant IRB/EC and obtaining written approval for this study. The approval will be obtained prior to the initiation of the study.

The approval for both the protocol and informed consent must specify the date of approval, protocol number and version, or amendment number.

Any amendments to the protocol after receipt of IRB/EC approval must be submitted by the Investigator to the IRB/EC for approval. The Investigator is also responsible for notifying the IRB/EC of any serious deviations from the protocol, or anything else that may involve added risk to subjects.

Any advertisements used to recruit subjects for the study must be reviewed and approved by the IRB/EC prior to use.

#### **11.4 Informed Consent**

The Investigator must obtain informed consent of a subject or his/her designee prior to any study related procedures as per GCPs as set forth in the CFR and ICH guidelines.

Documentation that informed consent occurred prior to the subject's entry into the study and the informed consent process should be recorded in the subject's source documents. The original consent form signed and dated by the subject and by the person consenting the subject prior to the subject's entry into the study, must be maintained in the Investigator's study files.

#### **11.5 Study Records Requirements**

The Investigator must ensure that the records and documents pertaining to the conduct of the study and the distribution of the study drug, that is copies of CRFs and source documents (original documents, data, and records [e.g., hospital records; clinical and office charts; laboratory notes; memoranda; subject's diaries or evaluation checklists; SAE reports, pharmacy dispensing records; recorded data from automated instruments; copies or transcriptions certified after verification as being accurate copies; microfiches; photographic negatives, microfilm, or magnetic media; x-rays; subject files; and records kept at the pharmacy, at the laboratories, and at medico-technical departments involved in the clinical study; documents regarding subject treatment and study drug accountability; original signed informed consents, etc.]) be retained by the Investigator for as long as needed to comply with national and international regulations (generally 2 years after discontinuing clinical development or after the last marketing approval). The Investigator agrees to adhere to the document/records retention procedures by signing the protocol.

